### **10.2.3 Investigational Product Compliance**

Review subject compliance with the IP usage and adjunct product usage and collect all used and unused study IPs and other products that were dispensed.

### **10.2.4 Adverse Event Collection: Safety Assessment**

Assess and record any adverse events that are observed or reported since the previous visit, including those associated with changes in concomitant medication dosing.

### **10.2.5 Slit Lamp Biomicroscopy: Safety Assessment**

SLE of the cornea, adnexa, and anterior segment must be performed in both eyes before instillation of any diagnostic eye drops.

### **10.2.6 Device Deficiencies: Safety Assessment**

Assess and record any device deficiencies that are reported or observed since the previous visit. Requirements for reporting device deficiencies in the study can be found in Section 11.

## 10.3 Unscheduled Visits

If a subject visit occurs between any regularly scheduled visit and the visit is conducted by study personnel, this visit must be documented as an unscheduled visit. If the subject seeks medical attention outside the clinic (for example, at an emergency room) or at the clinic but is seen by nonstudy personnel, the investigator is to capture adverse event-related information on the adverse event form upon becoming aware.

During all unscheduled visits, the investigator must conduct the following procedures:

- Collect adverse event information, as applicable
- Collect device deficiency information, as applicable
- Record changes in medical condition or concomitant medication

The investigator may perform additional procedures for proper diagnosis and treatment of the subject. The investigator must document this information in the subject's case history source documents.

If during an unscheduled visit the subject is discontinuing the IP or discontinuing from the study, the investigator must conduct Exit procedures according to Table 3-1 Schedule of Study Procedures and Assessments and Section 10.4.3, as possible.

A subject may come in for an unplanned lens replacement if needed. Unplanned lens replacement is to be used in the event that the subject has no additional spare study lenses and in the event of a device deficiency or if a lens is lost or damaged, so as to maintain study lens wear until the follow-up visit.

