BCVA with manifest refraction (OD, OS, logMAR distance)	X	(X)	(X)	(X)
Biomicroscopy	X	X	X	(X)

Procedure / Assessment	Visit 1 Screening / Baseline / Dispense	Visit 2 Day 4 Follow- up / Exit	Early Exit	Unscheduled Visit
	Day 1	Day 4 (-1/+1 Day)	N/A	N/A
Determine and record study lenses power (dispensed power, OD, OS)	X			
VA with study lenses (dispensed power) (OD, OS, logMAR distance)	X	X	(X)	(X)

Procedure / Assessment	Visit 1 Screening / Baseline / Dispense	Visit 2 Day 4 Follow- up / Exit	Early Exit	Unscheduled Visit
	Day 1	Day 4 (-1/+1 Day)	N/A	N/A
Unplanned lens replacement with reason		(X)		(X)
AEs	X	X	X	X
Device deficiencies	X	X	X	X
Exit Form	(X)	X	X	(X)

(X) Assessment performed as necessary, e.g., decrease of VA by 2 lines or more with investigational product

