## **8 STUDY POPULATION**

The study population consists of male and female subjects ages 18 and older with normal eyes (other than the need for optical correction for myopia) and who are successful spherical soft contact lens wearers in both eyes for a minimum of 5 days per week and 10 hours per day during the past 3 months. The eligible study population will be representative of the investigational product target population.

The aim is to enroll (consent) approximately 110 subjects at approximately 7 sites in the US, with 14 (intended minimum) to 16 (intended maximum) subjects per site, and a target of 100 total subjects completed. Site-specific targets may vary based upon individual site capabilities. [REDACTED]  
[REDACTED]  
[REDACTED]  
[REDACTED]

Estimated time needed to recruit subjects for the study is approximately 3 weeks; however, unanticipated circumstances may shorten or lengthen this time and would not require amendment of this protocol. Because a 5% screening failure rate is expected, approximately 110 subjects are targeted to be enrolled (consented).

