### **10.4.2 Discontinuations**

Discontinued subjects are individuals who voluntarily withdraw or are withdrawn from the study by the investigator after signing informed consent and after randomization to product/dispense of study product.

Subject numbers of discontinued subjects must not be re-used (i.e., subject replacement is not allowed).

Subjects may discontinue from study or study treatment at any time for any reason. Subjects may also be discontinued from study treatment at any time if, in the opinion of the investigator, continued treatment poses a risk to their health.

If a subject discontinues from study treatment, every effort must be made to keep the subject in the study and to continue with the study assessments as specified in the schedule of study procedures and assessments until the final visit.

For subjects discontinuing from the study, the investigator must complete all Exit procedures according to Table 3-1 Schedule of Study Procedures and Assessments and Section 10.4.3, if the subject is willing and able, and if in the opinion of the investigator it is safe for the subject to do so.

The investigator must document the reason for study or treatment discontinuation in the subject's case history source documents.

To ensure the safety of all subjects who discontinue early, investigators must assess each subject and, if necessary, advise them of any therapies and/or medical procedures that may be needed to maintain their health.

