### **10.4.3 Schedule of Procedures and Assessments for Subjects Discontinued from Investigational Product**

Other than screen failures, if a subject discontinues from the study, the subject should undergo an Early Exit Visit, as possible. Refer to Table 3-1 for the required Early Exit procedures.

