5.3.1 Adverse Events

The applicable definition of an AE is in the study protocol. All AEs occurring from when a subject signs informed consent to the time of their study exit will be accounted for in the reporting.

Presentation of AEs will be separated into pre-treatment AEs and treatment-emergent AEs as defined below:

- Pre-treatment AE: an event that occurs after signing informed consent but prior to exposure to study lenses.
- Treatment-emergent: an event that occurs from first exposure to study lenses until the subject exists from the study.

The following tables and supportive listings will be provided:

- Incidence of All Ocular Treatment-Emergent Adverse Events
- Incidence of Ocular Serious Treatment-Emergent Adverse Events
- Incidence of Ocular Significant Nonserious Treatment-Emergent Adverse Events
- Incidence of All Nonocular Treatment-Emergent Adverse Events
- Incidence of Nonocular Serious Treatment-Emergent Adverse Events
- Listing of All Ocular Treatment-Emergent Adverse Events
- Listing of All Nonocular Treatment-Emergent Adverse Events
- Listing of All Ocular Pre-Treatment Adverse Events
- Listing of All Nonocular Pre-Treatment Adverse Events

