10 APPENDIX

Table 10-1 Schedule of Study Procedures and Assessments

Procedure / Assessment	Visit 1 Screening / Baseline / Dispense	Visit 2 Day 4 Follow- up / Exit■	Early Exit	Unscheduled Visit
	Day 1	Day 4 (-1/+1 Day)	N/A	N/A
Informed Consent	X			
Demographics	X			
Medical History	X	X	X	X
Concomitant Medications	X	X	X	X
Inclusion/Exclusion	X			
Habitual lens (brand, power■)	X			
VA with habitual correction (OD, OS, Snellen distance)■	X	X	X	(X)
Keratometry	X			
Manifest refraction	X	(X)	(X)	(X)
BCVA with manifest refraction (OD, OS, logMAR distance)	X	(X)	(X)	(X)

Procedure / Assessment	Visit 1 Screening / Baseline / Dispense	Visit 2 Day 4 Follow- up / Exit■	Early Exit	Unscheduled Visit
	Day 1	Day 4 (-1/+1 Day)	N/A	N/A
Biomicroscopy	X	X	X	(X)
Determine and record study lenses power (dispensed power, OD, OS)	X			
VA with study lenses (dispensed power)■ (OD, OS, logMAR distance)	X	X	(X)	(X)

Procedure / Assessment	Visit 1 Screening / Baseline / Dispense	Visit 2 Day 4 Follow- up / Exit■	Early Exit	Unscheduled Visit
	Day 1	Day 4 (-1/+1 Day)	N/A	N/A
Unplanned lens replacement with reason		(X)		(X)
AEs	X	X	X	X
Device deficiencies	X	X	X	X

Procedure / Assessment	Visit 1 Screening / Baseline / Dispense	Visit 2 Day 4 Follow- up / Exit	Early Exit	Unscheduled Visit
	Day 1	Day 4 (-1/+1 Day)	N/A	N/A
Exit Form	(X)	X	X	(X)

(X) Assessment performed as necessary, e.g., decrease of VA by 2 lines or more with investigational product

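### Do the protocol's rules for a subject who stops the study lenses but stays in the study conflict in a way that affects the results?

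*Protocol*

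**What the plan says.** Three protocol sections deal with subjects who stop early.

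- **Section 10.3 (unscheduled visits):** "If during an unscheduled visit the subject is discontinuing the IP or discontinuing from the study, the investigator must conduct Exit procedures". The sentence refers to Table 3-1 and Section 10.4.3, and ends by limiting the duty to what is feasible.
- **Section 10.4.2 (discontinuations):** "If a subject discontinues from study treatment, every effort must be made to keep the subject in the study", with scheduled assessments continuing to the last visit. A separate paragraph requires exit procedures of subjects who leave the study.
- **Section 10.4.3:** the heading is "Schedule of Procedures and Assessments for Subjects Discontinued from Investigational Product", but the rule beneath it reads "Other than screen failures, if a subject discontinues from the study, the subject should undergo an Early Exit Visit, as possible".

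In Table 3-1, repeated as SAP Table 10-1, visual acuity (VA) with the study lenses is required at Visit 2 and as needed at Early Exit and at unscheduled visits. Biomicroscopy is required at both Visit 2 and Early Exit. The Exit Form is required at Visit 2 and Early Exit, and as needed at an unscheduled visit.

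On adverse events, SAP Section 5.3.1 says "All AEs occurring from when a subject signs informed consent to the time of their study exit will be accounted for in the reporting", and its treatment-emergent window closes at the same point. Protocol Section 11.6 separately asks investigators to pass on new safety information, including new events, and to record follow-up of ongoing events in the eCRF up to database lock.

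**The concern.** Consider a subject who stops the lenses at an unscheduled visit but does not withdraw. Section 10.3 seems to send this subject through exit, while Section 10.4.2 seems to keep the subject until Visit 2. Section 10.4.3 ought to settle the matter but does not, because its heading and its rule describe different people.

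The reading decides which column of the schedule applies. Study-lens VA is the primary variable, and it is mandatory in one column and discretionary in the other. The end of the adverse event window also depends on when the subject is taken to have exited. With about 7 sites, the same event could be closed out at one and followed up at another. Subjects who stop the lenses are also those whose safety follow-up is most informative. If the conflict were real and material, the safety description would be uneven across sites and some Day 4 data would be lost.

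**Working it through.** **1. Can both rules be obeyed?** Section 10.3 requires exit *procedures*; it does not say that participation ends. Section 10.4.2 asks for continued participation. A site can do the exit assessments when the lenses stop and still see the subject at Visit 2, and nothing in the visible text forbids that order. Marking the Exit Form as needed in the unscheduled-visit column fits this reading. The text does not spell the order out.

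**2. What would exit at the unscheduled visit cost?**

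| Item | If handled as exit | If followed to Visit 2 |
|---|---|---|
| Biomicroscopy | Required, done earlier | Required at Visit 2 |
| Study-lens VA | As needed | Required, but the subject may no longer wear the lenses |
| Adverse events | Reported window closes at exit; Section 11.6 still asks for new and ongoing events | Window closes at Visit 2 |

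A post-exposure eye examination is required either way, and Section 12.6 counts grade increases at any visit after baseline. Study-lens VA may be unobtainable under either reading. Only the closing date of the treatment-emergent window moves. For a subject stopping on Day 1 or 2, with Visit 2 on Day 3 to 5, the shift is from 3 − 2 = 1 day to 5 − 1 = 4 days.

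**3. How many subjects?** The documents give no figure for subjects who stop the lenses but stay. The nearest scale is implied non-completion: Section 8 enrols about 110 with 5% screen failure and targets 100 completers, so 110 × 0.95 = 104.5 and 104.5 − 100 = 4.5. If nobody fails screening the figure is 110 − 100 = 10. These are non-completers, a different group, and serve here only as a stress test.

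**4. Does it touch the primary result?** Inputs are the SD of the paired difference, 0.0567, the margin of 0.05 logMAR and one-sided α = 0.05 (Protocol Section 3; SAP Section 7). A true difference of 0 is assumed.

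- *The plan's own figure.* A one-sided paired t-test with the noncentral t gives 82.3% power at N = 10, which reproduces the stated 10 for 80%. For 90% it gives N = 13 (91.1%) against the stated 14 (93.0%), a small and conservative difference.
- *Upper limit with 100 completers.* 0 + 1.660 × 0.0567/√100 = 0.0094.
- *With only 80 pairs.* The same calculation gives 0.0106.
- *Adding k leavers with mean difference d.* Let N = 100 + k. The mean is kd/N, the variance is 0.0567² + (100k/N)d²/(N − 1), and the upper limit is mean + t × SD/√N. For k = 5 and d = 0.584:
  - mean = 5 × 0.584/105 = 0.0278
  - SD = √(0.00321 + 4.762 × 0.341/104) = 0.137
  - limit = 0.0278 + 1.660 × 0.137/√105 = 0.050

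| Leavers | d that brings the limit to 0.05 | Multiple of the margin |
|---|---|---|
| 4 | 0.688 | 13.8 |
| 5 | 0.584 | 11.7 |
| 10 | 0.349 | 7.0 |

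At d = 0.20 the limit is only 0.019 with 4 leavers and 0.021 with 5. These figures use a simple paired comparison at Day 4 in place of the planned mixed model.

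**The case for a change.** The strongest case for a change is that the sections differ on their face and none is given precedence. The feasibility qualifier in Section 10.3 excuses what cannot be done, but does not remove the trigger on stopping the product. The sequential reading has to be inferred, and the mandatory Exit Form in the Early Exit column points towards closing the subject out. Section 11.6 keeps safety information flowing without fixing the exit date that bounds the reported tables. One could add that the visible text does not say how the Visit 2 VA row is recorded for someone no longer wearing the lenses, or whether an Early Exit value within the Day 4 window counts as Day 4.

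The wording point stands: the three passages are not aligned, and the mismatch in Section 10.4.3 is a drafting slip. The claim of harm does not stand. Adverse event collection does not stop at exit, and a post-exposure biomicroscopy is not lost. The recording and windowing questions cannot be judged missing. Blacked-out marks sit on the Visit 2 heading and the study-lens VA row of SAP Table 10-1, SAP Section 4 is partly redacted, and the Manual of Procedures and the Deviations and Evaluability Plan are not available here. Even if these details are absent, analysts can settle them before unmasking without altering the analysis.

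**Conclusion.** No change to the plan is needed. The sections are unevenly worded for a subject who stops the lenses but stays, yet they can be followed in sequence, and the plan as written still gives sound results. What remains is 1 to 4 days of uncertainty, for a subject stopping on Day 1 or 2, about which late-onset events are tabulated as treatment-emergent. It affects descriptive safety tables only, for a number of subjects that is unknown and may be zero. The noninferiority conclusion is unaffected: under the planned SD and no true difference, the upper limit is about 0.009 with 100 completers, and 10 leavers would need a mean difference of about 0.35 logMAR to bring it to the margin.

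This rests on reading exit procedures in Section 10.3 as assessments rather than as the end of participation, and on sites acting on Section 11.6. If the protocol is reopened for another reason, the three passages could be reconciled as an editorial matter. Which handling applies is the sponsor's decision.

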## 10.4 Discontinued Subjects

### 10.4.1 Screen Failures

Subjects who were excluded from the study after signing the informed consent and prior to randomization to product/dispense of study product.

The investigator must document the reason for screen failure in the subject's case history source documents.

Subject numbers must not be re-used.

### **10.4.2 Discontinuations**

Discontinued subjects are individuals who voluntarily withdraw or are withdrawn from the study by the investigator after signing informed consent and after randomization to product/dispense of study product.

Subject numbers of discontinued subjects must not be re-used (i.e., subject replacement is not allowed).

Subjects may discontinue from study or study treatment at any time for any reason. Subjects may also be discontinued from study treatment at any time if, in the opinion of the investigator, continued treatment poses a risk to their health.

If a subject discontinues from study treatment, every effort must be made to keep the subject in the study and to continue with the study assessments as specified in the schedule of study procedures and assessments until the final visit.

For subjects discontinuing from the study, the investigator must complete all Exit procedures according to Table 3-1 Schedule of Study Procedures and Assessments and Section 10.4.3, if the subject is willing and able, and if in the opinion of the investigator it is safe for the subject to do so.

The investigator must document the reason for study or treatment discontinuation in the subject's case history source documents.

To ensure the safety of all subjects who discontinue early, investigators must assess each subject and, if necessary, advise them of any therapies and/or medical procedures that may be needed to maintain their health.

### **10.4.3 Schedule of Procedures and Assessments for Subjects Discontinued from Investigational Product**

Other than screen failures, if a subject discontinues from the study, the subject should undergo an Early Exit Visit, as possible. Refer to Table 3-1 for the required Early Exit procedures.

## **10.5 Clinical Study Termination**

The study sponsor reserves the right to suspend or close the investigational site or suspend or terminate the study in its entirety at any time.

If the clinical study is prematurely terminated or suspended by the study sponsor:

- The study sponsor must:
  - Immediately notify the investigator(s) and subsequently provide instructions for study termination.
  - Inform the investigator and the regulatory authorities of the termination/suspension and the reason(s) for the termination/suspension.
- The investigator must:
  - Promptly notify the IRB/IEC of the termination or suspension and of the reasons.
  - Provide subjects with recommendations for poststudy treatment options as needed.

The investigator may terminate the site's participation in the study for reasonable cause.

Breaking of the masked treatment codes will be done after locking the database.

### **10.5.1 Follow-up of subjects after study participation has ended**

Following this study, the subject will return to their eye care professional for their routine eye care.

[figure not shown]
## **11 ADVERSE EVENTS AND DEVICE DEFICIENCIES**

### **11.1 General Information**

An AE is any untoward medical occurrence, unintended disease or injury, or untoward clinical signs (including abnormal laboratory findings) in subjects, users, or other persons, whether or not related to the investigational medical device (test product). Refer to the Glossary of Terms and figures below for categories of AEs and SAEs.

[figure not shown]
**Figure 11-1**

**Categorization of All Adverse Events**

**Figure 11-2**

**Categorization of All Serious Adverse Events**

### **Specific Events Relevant to this Protocol**

#### ***Serious Adverse Events***

In addition to reporting all AEs (serious and nonserious) meeting the definitions, the Investigator must report any occurrence of the following as an SAE:

- An ocular infection including a presumed infectious ulcer with any of the following characteristics:

- Central or paracentral location
- Penetration of Bowman's membrane
- Infiltrates >2 mm diameter
- Iritis
- Increase in intraocular pressure
- Culture positive for microorganisms
- Increasing size or severity at subsequent visits
- Any central or paracentral corneal event (such as neovascularization) that results in permanent opacification
- Hypopyon
- Hyphema
- Neovascularization within the central 6 mm of the cornea
- Permanent vision loss as defined by loss of 2 or more lines of BCVA from enrollment visit that fails to resolve
- Uveitis (anterior, intermediate, or posterior)
- Corneal abrasion affecting ≥50% of corneal surface area

### ***Significant Nonserious Adverse Events***

A significant nonserious AE is a device-related, nonsight threatening adverse event that warrants discontinuation of any contact lens wear for greater than or equal to 2 weeks. In addition, the Investigator must report any occurrence of the following as a Significant Nonserious Adverse Event:

- Peripheral non-progressive non-infectious ulcers
- All symptomatic corneal infiltrative events
- Corneal staining score greater than or equal to grade 3 (Refer to MOP for grading scales. Grading scale is based on ISO 11980:2012 unless specified differently in MOP).
- Temporary vision loss as defined by loss of 2 or more lines of BCVA from enrollment visit that persists for 2 or more weeks

- Neovascularization score greater than or equal to grade 2 (Refer to MOP for grading scales. Grading scale is based on ISO 11980:2012 unless specified differently in MOP).

*The above events are based on the categories provided in the ISO 11980 and the US FDA Premarket Notification (510(k)) Guidance Document for Daily Wear Contact Lenses.*

### ***Device Deficiencies***

A device deficiency is inadequacy of a medical device with respect to its identity, quality, durability, reliability, safety, or performance. A device deficiency may or may not be associated with patient harm (i.e., ADE or SADE); however, not all ADEs or SADEs are due to a device deficiency. The Investigator should determine the applicable category listed in the device deficiency eCRF for the identified or suspect device deficiency and report any patient harm separately. Examples of device deficiencies include the following:

- Failure to meet product specifications (e.g., incorrect lens power/diameter/base curve/color)
- Lens/solution cloudy
- Lens surface/edge defect
- Torn lens during handling/in pack
- Packaging deficit (e.g., mislabeled product, tampered seal, leaking bottle/container)
- Suspect product contamination
- Lack of performance

### **11.2 Monitoring for Adverse Events**

At each visit, after the subject has had the opportunity to spontaneously mention any problems, the Investigator should inquire about AEs by asking the standard questions shown below and report as applicable:

- “Have you had any health problems since your last study visit?”
- “Have there been any changes in the medicines you take because of a new health issue since your last study visit?”

In addition, changes in *any protocol-specific parameters and/or questionnaires* evaluated during the study are to be reviewed by the Investigator. Any untoward (unfavorable and unintended) change in *a protocol-specific parameter or questionnaire response* that is

clinically relevant, in the opinion of the Investigator, is to be reported as an AE. These clinically relevant changes will be reported regardless of causality.

